#### 9.10.4. Holding rules

The safety holding rules which will be assessed by the investigator are defined in [Table 22](#) and the safety holding rules which will be assessed by the iSRC or IDMC during the safety evaluation are defined in [Table 23](#).

**Table 22 Holding rules assessed by the investigator**

Holding Rule	Event	Number of infants/group
1a	Death or any life-threatening serious adverse event (SAE) that can be causally related to vaccination, according to investigator's assessment.	≥ 1
1b	Any withdrawal from the study (by investigator or parent(s)/LAR(s) of the subject request) following a Grade 3 AE that cannot reasonably be attributed to a cause other than vaccination.	≥ 1
1c	Any local or general solicited AE leading to hospitalization that cannot reasonably be attributed to a cause other than vaccination.	≥ 1
1d	Within 30 days post-vaccination (Visit 1 and Visit 3), Any spontaneous local or general bleeding AND Thrombocytopenia < 50000/mm 	≥ 1

If an investigator detects one of the holding rules mentioned above, he/she will immediately put the enrolment or the vaccination on hold (refer to Section [9.10.4](#)) and he/she will immediately inform the sponsor and enter the data in the eCRF. It is sponsor's responsibility to put the enrolment or the vaccination on hold at all sites.

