#### **9.2.5. Subject hospitalized for LRTI**

Subjects admitted to hospital and treated for an LRTI will be documented fully as SAEs. In addition, to establish the severity of the illness, the eCRF screen corresponding to the assessment visit will be completed as fully as possible from medical records. Signs and symptoms to be recorded in the eCRF are listed in the SPM, and include where available oxygen saturation in air. Study staff will collect a nasal swab for all the subjects who have been hospitalized with a RTI for analysis at sponsor laboratory. All subjects with clinical suspicion of LRTI must be tested for RSV and RVP using locally available test.

Study staff will also collect a blood sample to be stored at sponsor's laboratory for future assessment of mechanism of illness (potential ERD). This will be required to be done only for RSV-positive subjects using a locally available RSV test.

**9.3. Detecting and recording adverse events, adverse events of special interest and serious adverse events****9.3.1. Time period for detecting and recording adverse events, adverse events of special interest and serious adverse events**

All AEs starting within 30 days following administration of each dose of study vaccine (Day 1 to Day 30) must be recorded into the appropriate section of the eCRF, irrespective of intensity or whether or not they are considered vaccination-related.

The time period for collecting and recording SAEs will begin at the first receipt of study vaccine and will end at study conclusion. See Section [9.4](#) for instructions on reporting of SAEs.

All AEs/SAEs leading to withdrawal from the study will be collected and recorded from the time of the first receipt of study vaccine.

In addition to the above-mentioned reporting requirements and in order to fulfil international reporting obligations, SAEs that are related to study participation (i.e., protocol-mandated procedures, invasive tests, a change from existing therapy) or are related to a concurrent GSK medication/vaccine will be collected and recorded from the time the subject consents to participate in the study until she/he is discharged from the study.

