**Table 23 Holding rules during the planned iSRC or IDMC evaluation**

Holding Rule	Event	Number of infants
2a	Any Grade 3 solicited local AE lasting 48 hours or more following administration of an investigational RSV vaccine, within the 7-day (Days 1-7) post-vaccination period.	≥ 25% & ≥ 2 infants in any of two pooled RSV vaccine groups
2b	Any Grade 3 solicited general AE lasting 48 hours or more following administration of an investigational RSV vaccine, that cannot reasonably be attributed to a cause other than vaccination, within the 7-day (Days 1-7) post-vaccination period.	≥ 25% & ≥ 2 infants in any of two pooled RSV vaccine groups
2c	Any ≥ Grade 3 unsolicited AE following administration of an investigational RSV vaccine, that cannot reasonably be attributed to a cause other than vaccination, within the 7-day (Days 1-7) post-vaccination period	≥ 25% & ≥ 2 infants in any of two pooled RSV vaccine groups
2d	Infants hospitalized for RSV-LRTI	≥ 6 (in the combination of two pooled RSV vaccine and the pooled comparator/Placebo groups)

Of note, no formal holding rules will be applied for other safety data collected. However, these data will also be reviewed by the iSRC and the IDMC in order to allow for an overall assessment of the benefit/risk ratio of vaccination.

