**10.2.1. Subject withdrawal from the study**

From an analysis perspective, a ‘withdrawal’ from the study refers to any subject who did not come back for the concluding visit foreseen in the protocol.

All data collected until the date of withdrawal/last contact of the subject will be used for the analysis.

A subject is considered a ‘withdrawal’ from the study when no study procedure has occurred, no follow-up has been performed and no further information has been collected for this subject from the date of withdrawal/last contact.

Investigators will make an attempt (e.g., three telephone calls and a certified letter to the last known address) to contact those subjects who do not return for scheduled visits or follow-up.

Information relative to the withdrawal will be documented in the eCRF. The investigator will document whether the decision to withdraw a subject from the study was made by the subject's parent(s)/LAR(s), or by the investigator, as well as which of the following possible reasons was responsible for withdrawal:

- Serious adverse event.
- Unsolicited non-serious adverse event.
- Solicited adverse event
- Protocol violation (specify).
- Consent withdrawal, not due to an adverse event\*.
- Moved from the study area.
- Lost to follow-up.
- Other (specify).

\*In case a subject is withdrawn from the study because he/she/the subject's parent(s)/LAR(s) has withdrawn consent, the investigator will document the reason for withdrawal of consent, if specified by the subject/subject's parent(s)/LAR(s), in the eCRF.

Subjects who are withdrawn from the study because of SAEs/AEs must be clearly distinguished from subjects who are withdrawn for other reasons. Investigators will follow subjects who are withdrawn from the study as result of a SAE/AE until resolution of the event (see Section 9.5.1.1).

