#### **10.2.2. Subject withdrawal from study vaccine**

A 'withdrawal' from the study vaccine refers to any subject who does not receive the complete treatment, i.e., when no further planned dose is administered from the date of withdrawal. A subject withdrawn from the study vaccine may not necessarily be withdrawn from the study as further study procedures or follow-up may be performed (safety or immunogenicity) if planned in the study protocol. The investigator should make all efforts to ensure that the subjects remain in the study to ensure a proper safety follow-up and medical care if needed.

Information relative to premature discontinuation of the study vaccine will be documented on the Vaccine Administration page/screen of the /eCRF. The investigator will document whether the decision to discontinue further vaccination/treatment was made by the subject's parent(s)/LAR(s) or by the investigator, as well as which of the following possible reasons was responsible for withdrawal:

- Serious adverse event.
- Unsolicited non-serious adverse event.
- Solicited adverse event
- Not willing to be vaccinated
- Other (specify).

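### Holding rule 1b turns on withdrawal from the study, so the same attributed Grade 3 AE counts if the family leaves but not if the infant stays in follow-up off vaccine; AE collection has a matching gap after Day 30

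*Protocol*

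**What the plan says.** Section 9.10.4, Table 22, lists the rules that the investigator applies. Rule 1b has a threshold of one infant per group and no time window. Its trigger is "Any withdrawal from the study (by investigator or parent(s)/LAR(s) of the subject request) following a Grade 3 AE", where the AE cannot reasonably be put down to anything but vaccination. On meeting it, the investigator must hold enrolment or vaccination at once.

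Section 10.2 has two categories of withdrawal.

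- **From the study (10.2.1).** For analysis, "a ‘withdrawal’ from the study refers to any subject who did not come back for the concluding visit foreseen in the protocol". A second sentence describes a withdrawn subject as one for whom, after last contact, "no study procedure has occurred, no follow-up has been performed and no further information has been collected for this subject". The section also states: "Investigators will follow subjects who are withdrawn from the study as result of a SAE/AE until resolution of the event".
- **From study vaccine (10.2.2).** This covers infants who do not complete dosing. Solicited and unsolicited AEs are among the listed reasons, and the reason is entered on the Vaccine Administration page. "A subject withdrawn from the study vaccine may not necessarily be withdrawn from the study as further study procedures or follow-up may be performed". Investigators are asked to do what they can to keep these infants in the study. Section 7.5 points the same way: an infant barred from further doses may go on with other procedures.

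On collection, Section 9.3.1 requires AEs starting within 30 days of each dose and then adds: "All AEs/SAEs leading to withdrawal from the study will be collected and recorded from the time of the first receipt of study vaccine". Tables 7 and 19 carry the same category. None of the three has a category for AEs leading to the stopping of study vaccine.

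The committee rules for Grade 3 AEs (Table 23, 2a-2c) have the threshold "≥ 25% & ≥ 2 infants in any of two pooled RSV vaccine groups".

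**The concern.** Two infants can have the same vaccine-attributed Grade 3 reaction after Dose 1, and both sets of parents can decline Dose 2. One family leaves the study; the other stays in follow-up, as 10.2.2 encourages. The first infant meets rule 1b and the second does not. Whether this one-infant hold fires then depends partly on retention, and a site that retains its families well will meet the rule less often.

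Investigators apply the rule themselves and immediately. Section 9.10 gives as the reason for the holding rules that the vaccine has never been given to potentially RSV-naive infants. The trigger should therefore be clear for the case that the protocol's own retention instruction makes likely.

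The recording side matters for a different reason. An event that is not collected as an AE cannot be restored by any later analysis plan.

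**Working it through.** **1. One event, two outcomes.**

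| After an attributed, non-serious Grade 3 AE | Category in 10.2 | Rule 1b |
|---|---|---|
| Family leaves the study | Withdrawal from the study (10.2.1) | Met |
| Dosing stops, infant stays in follow-up | Withdrawal from study vaccine (10.2.2) | Not met |

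**2. Other rules that might catch the retained infant.** Rule 1a needs death or a life-threatening SAE. Rule 1c needs a solicited AE leading to hospitalization. Rule 1d needs spontaneous bleeding with platelets below 50000/mm³ within 30 days of Visit 1 or Visit 3. Rules 2a-2c count only Days 1-7, and 2a and 2b only events lasting at least 48 hours. With a pooled group of 50 as the denominator, 25% is 0.25 × 50 = 12.5, so 13 infants are needed (12 of 50 is 24%).

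A non-serious Grade 3 AE that is not an AESI is not on the 48-hour lists in 9.10.2 and 9.10.3. It reaches the committees through the four-weekly iSRC review and the monthly IDMC summaries.

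**3. The plan's own figure.** Section 11.4 gives about 92% for at least one SAE among 50 infants at a true rate of 5%. Check: 1 − 0.95^50 = 0.923, which agrees. Rule 1b also has a threshold of one, so the same formula applies to it.

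**4. Size, as an illustration.** Let p be the rate of attributed Grade 3 AEs that stop dosing, and f the share of those infants who also leave the study. Both are assumptions; the protocol gives neither. For one group of 50, P(1b fires) = 1 − (1 − p·f)^50.

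| p | f = 100% | 50% | 25% | 10% | 0 |
|---|---|---|---|---|---|
| 2% | 63.6% | 39.5% | 22.2% | 9.5% | 0% |
| 5% | 92.3% | 71.8% | 46.7% | 22.2% | 0% |
| 10% | 99.5% | 92.3% | 71.8% | 39.5% | 0% |

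For comparison, the binomial probability of at least 13 events among 50 is 7.5 × 10⁻⁷ at a rate of 5%, 0.1% at 10% and 18.6% at 20%. This supposes that every event meets the timing and duration conditions and falls under one rule.

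**5. The recording gap.** The AE period after Dose 1 ends on Day 30. Table 24 allows Visit 3 at 23 to 44 days after Visit 1, that is Day 24 (1 + 23) to Day 45 (1 + 44). With a delayed Visit 3, an AE can start on Days 31 to 44, or on Day 45 before the injection, and be the reason Dose 2 is not given. If it is non-serious, not an AESI, and the infant stays in the study, it fits no collection category in 9.3.1. What remains is the reason category on the Vaccine Administration page.

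**The case against.** The strongest reply is that nothing here conflicts. Rule 1b, 10.2.1 and 10.2.2 give the same literal answer for a retained infant: not a study withdrawal, so 1b is not met. A reader might infer that the rule misses the very infants it was written to catch. The protocol states no purpose for 1b, so that goes beyond the text. The rule is not empty either, since families who leave do trigger it. What stands is that its outcome depends on retention and that the protocol does not say whether this is intended.

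Other strong inferences also fail.

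- **That a study withdrawal can be known only at the concluding visit.** That definition is expressly for analysis. Rule 1b is worded around a decision by the investigator or parents, and 10.2.1 has the decision-maker and reason documented.
- **That follow-up to resolution cancels the withdrawal.** Section 9.5.1.1 places such follow-up after discharge from the study, and 10.2.1 itself calls these infants withdrawn. The sentence about no further information is loose drafting at most.
- **That 1b is the only one-infant rule able to catch a non-serious Grade 3 event.** Rule 1d requires neither seriousness nor attribution, and platelets below 50000/mm³ are Grade 3 or worse in Table 28.
- **That nothing else can stop vaccination.** Section 9.10.5 provides for a hold by the investigator, iSRC or IDMC for a safety concern, and 9.10.2 and 9.10.3 require an immediate hold on any other safety signal. These routes rest on judgement rather than a count, but they are real.

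On recording, the objection is that AEs within 30 days are collected and Grade 3 related AEs are tabulated, that the 30-day limit is the protocol's own endpoint window, and that an extra table can be left to the SAP. All of this is fair for events up to Day 30. It does not answer the later case: the protocol fixes what is collected, and it already goes beyond 30 days for AEs leading to study withdrawal.

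**Conclusion.** The point holds in a limited form. Rule 1b covers an attributed Grade 3 AE when the infant leaves the study and not when dosing stops and the infant is retained, which is the course 10.2.2 encourages. The counted committee rules do not fill that space: they need 13 infants at full enrolment of 50 per group and look only at Days 1-7. Holds for a safety concern remain available. The probabilities above show how far retention can move the trigger; they rest on assumed values of p and f and are not estimates for this trial.

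The recording gap is narrow but definite. It concerns non-serious, non-AESI events starting after Day 30 and before a delayed Visit 3, in infants who then miss Dose 2 and stay in the study. This is a worthwhile correction at the next amendment, not a condition for the trial to proceed.

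**What to change.** 1. In Section 9.3.1 and Tables 7 and 19, add AEs leading to discontinuation of study vaccine, collected from the first dose whatever the 30-day window. In Section 11.8.1, tabulate them by pooled group. The reason category is already entered on the Vaccine Administration page, so the addition is the AE record behind it.
2. Reconcile the wording of rule 1b with Sections 10.2.1 and 10.2.2, so that its application to an infant stopped from vaccine but kept in follow-up is explicit. Which trigger applies is for the sponsor and IDMC to decide; this review proposes none.

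The cost is protocol wording and one extra safety table, with no added visits or infants. If the reconciled trigger is broader, holds may become more frequent.

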**Table 23 Holding rules during the planned iSRC or IDMC evaluation**

Holding Rule	Event	Number of infants
2a	Any Grade 3 solicited local AE lasting 48 hours or more following administration of an investigational RSV vaccine, within the 7-day (Days 1-7) post-vaccination period.	≥ 25% & ≥ 2 infants in any of two pooled RSV vaccine groups
2b	Any Grade 3 solicited general AE lasting 48 hours or more following administration of an investigational RSV vaccine, that cannot reasonably be attributed to a cause other than vaccination, within the 7-day (Days 1-7) post-vaccination period.	≥ 25% & ≥ 2 infants in any of two pooled RSV vaccine groups
2c	Any ≥ Grade 3 unsolicited AE following administration of an investigational RSV vaccine, that cannot reasonably be attributed to a cause other than vaccination, within the 7-day (Days 1-7) post-vaccination period	≥ 25% & ≥ 2 infants in any of two pooled RSV vaccine groups
2d	Infants hospitalized for RSV-LRTI	≥ 6 (in the combination of two pooled RSV vaccine and the pooled comparator/Placebo groups)

Of note, no formal holding rules will be applied for other safety data collected. However, these data will also be reviewed by the iSRC and the IDMC in order to allow for an overall assessment of the benefit/risk ratio of vaccination.

#### Risk assessment

[Figure 4](#) gives the probability of not meeting holding rule assessed by the investigator and the sponsor when 30 or 50 subjects are enrolled per study group.

**Figure 4 Evaluations based on 30 or 50 enrolled subjects - Risk assessment curve for one formulation based on the proposed safety holding rules assessed by the investigator and the sponsor**

[figure not shown]
[figure not shown]

Figure 5 gives the probability of not meeting holding rule assessed during the planned IDMC evaluation when 50 subjects are enrolled per study group and 150 subjects in the whole trial.

**Figure 5 Evaluations based on 50 subjects per group - Risk assessment curve for one formulation based on the proposed safety holding rules during the planned IDMC evaluation**

**9.10.5. Procedure if the trial is put on hold**

If the trial is put on hold by the investigator *or* iSRC or IDMC because a pre-defined holding rule is met or because of a safety concern, then all enrolment in the study and all vaccination will cease immediately, but all other procedures relating to safety, immunology and disease monitoring will continue. The iSRC/IDMC will review all available safety information and may ask for additional information to be provided by the investigators or the study team. The iSRC/IDMC will make a recommendation to the study team whether the study should be stopped permanently, modified or continued unchanged.

The VSMB will review all data and iSRC/IDMC recommendation and will decide whether to stop permanently, modify or continue the conduct of the study. The decision of the VSMB regarding the further conduct of the study will be documented and provided in writing to the investigators.

**10. SUBJECT COMPLETION AND WITHDRAWAL****10.1. Subject completion**

A subject who returns for the concluding visit foreseen in the protocol is considered to have completed the study.

**10.2. Subject withdrawal**

Withdrawals will not be replaced.

**10.2.1. Subject withdrawal from the study**

From an analysis perspective, a ‘withdrawal’ from the study refers to any subject who did not come back for the concluding visit foreseen in the protocol.

All data collected until the date of withdrawal/last contact of the subject will be used for the analysis.

A subject is considered a ‘withdrawal’ from the study when no study procedure has occurred, no follow-up has been performed and no further information has been collected for this subject from the date of withdrawal/last contact.

Investigators will make an attempt (e.g., three telephone calls and a certified letter to the last known address) to contact those subjects who do not return for scheduled visits or follow-up.

Information relative to the withdrawal will be documented in the eCRF. The investigator will document whether the decision to withdraw a subject from the study was made by the subject's parent(s)/LAR(s), or by the investigator, as well as which of the following possible reasons was responsible for withdrawal:

- Serious adverse event.
- Unsolicited non-serious adverse event.
- Solicited adverse event
- Protocol violation (specify).
- Consent withdrawal, not due to an adverse event\*.
- Moved from the study area.
- Lost to follow-up.
- Other (specify).

\*In case a subject is withdrawn from the study because he/she/the subject's parent(s)/LAR(s) has withdrawn consent, the investigator will document the reason for withdrawal of consent, if specified by the subject/subject's parent(s)/LAR(s), in the eCRF.

Subjects who are withdrawn from the study because of SAEs/AEs must be clearly distinguished from subjects who are withdrawn for other reasons. Investigators will follow subjects who are withdrawn from the study as result of a SAE/AE until resolution of the event (see Section 9.5.1.1).

#### **10.2.2. Subject withdrawal from study vaccine**

A 'withdrawal' from the study vaccine refers to any subject who does not receive the complete treatment, i.e., when no further planned dose is administered from the date of withdrawal. A subject withdrawn from the study vaccine may not necessarily be withdrawn from the study as further study procedures or follow-up may be performed (safety or immunogenicity) if planned in the study protocol. The investigator should make all efforts to ensure that the subjects remain in the study to ensure a proper safety follow-up and medical care if needed.

Information relative to premature discontinuation of the study vaccine will be documented on the Vaccine Administration page/screen of the /eCRF. The investigator will document whether the decision to discontinue further vaccination/treatment was made by the subject's parent(s)/LAR(s) or by the investigator, as well as which of the following possible reasons was responsible for withdrawal:

- Serious adverse event.
- Unsolicited non-serious adverse event.
- Solicited adverse event
- Not willing to be vaccinated
- Other (specify).

### **10.3. Extension study**

During the study conclusion visit, the investigator will ask each subject's parent(s)/LAR(s) if they are interested to allow the subject to participate in a booster study/long-term study. If subject's parent(s)/LAR(s) is/are not interested in participating in the booster study/long-term study the reason for refusal will be documented in the subject's eCRF.

### **10.4. Screen and baseline failures**

Screening failures are defined as subjects who are withdrawn from the study after giving informed consent, but who do not meet the inclusion and exclusion criteria.

The following information will be collected for screening failures:

- Informed consent.
- Inclusion/exclusion criteria.
- Demographic data.
- Medical history.
- Physical examination.
- Growth monitoring.
- Blood samples for hematology and biochemistry and humoral response.
- SAEs related to study participation, to concomitant use of GSK products or any fatal SAEs.
- Screening conclusion.

